##### 13.2.8.1 PRIMARY EFFICACY ANALYSIS

The primary efficacy analysis will be on the change in Investigator-administered MADRS total score from Visit 2 (baseline) to the last visit of the 8-week double-blind treatment period Visit 7 (week 8). The key comparison will be the contrast between BTRX-246040 and placebo at Visit 7 (week 8) from a mixed-model repeated measures (MMRM) analysis. The primary analysis will use the Full Analysis Set.

A repeated measures analysis refers to a restricted-maximum-likelihood- (REML-) based, MMRM analysis using all the longitudinal observations at each post-baseline visit. The model for this analysis will include the fixed class effects of treatment, investigative site, visit, and treatment-by-visit interaction, as well as the continuous, fixed covariates of baseline Investigator-administered MADRS total score. An unstructured covariance structure will be used to model the within-patient errors. If the unstructured covariance matrix results in a lack of convergence, the heterogeneous autoregressive variance-covariance structure will be used. Least-square means (LS Means) for the difference to placebo at Week 8, with corresponding 2-sided 95% confidence intervals will be presented in tabular and graphical displays.

#### 13.2.8.2 SENSITIVITY ANALYSIS OF THE PRIMARY EFFICACY ENDPOINT

The following sensitivity analyses will be conducted on the primary efficacy endpoint to ensure robustness of the primary analysis.

The first sensitivity analysis will use the same mixed model repeated measures (MMRM) analysis used for the primary efficacy endpoint. The change from baseline in Investigator-administered MADRS total score at each post-baseline visit will be analyzed to provide information on the onset and the time course of efficacy. No imputation will be applied to missing data.

The second sensitivity analysis will utilize an ANCOVA method. This ANCOVA model will be used to analyze the change in Investigator-administered MADRS total score from baseline to Visit 7 (week 8). This ANCOVA model will include treatment group and investigative site as fixed effects and baseline MADRS total score as a covariate. The ANCOVA will be applied utilizing two methods of imputation for missing values.

- Multiple imputation for missing values: The results from the ANCOVA on multiple imputed datasets will be combined using the usual Rubin's rules for multiple imputation.
- Single imputation for missing values: The last observation carried forward (LOCF) imputation will be used.

The primary endpoint will be also analyzed based on the Per-Protocol Analysis Set, the Completer Analysis Set, and the MADRS Non-responders at Week 2 Analysis Set using MMRM.

An analysis of change from baseline in the computer-administered MADRS will also be performed using MMRM.

#### 13.2.8.3 SECONDARY EFFICACY ANALYSES

The analysis of the secondary and exploratory endpoints will be based on the Full Analysis Set. All statistical tests will be 2-sided with a significance level of 10%. Where appropriate, secondary efficacy analyses will report nominal p-values to aid the interpretation of results. No adjustments for multiplicity will be made for these secondary analyses.

Analysis of each of the secondary efficacy variables will be based on patients with available data at respective time points used in defining the specific secondary efficacy variable. Missing data for secondary endpoints will not be imputed.

The MMRM models used for the primary efficacy endpoint will be used to analyze continuous secondary efficacy endpoints collected longitudinally similar to the primary endpoint (#1-6 listed below). The MMRM models will contain fixed effects for treatment, investigative site, visit, and treatment-by-visit interaction as well as the continuous fixed covariates of baseline measurement. Change from baseline will be the response parameter of interest.

The following secondary efficacy endpoints will be analyzed by the MMRM model:

1. Change from baseline to Week 8 on the Investigator-administered MADRS-6 subscale
2. Change from baseline to Week 8 on the Investigator-administered MADRS individual items
3. Change from baseline to Week 8 on the total scores of the HADS subscales, the anxiety subscale (HADS-A) and the depression subscale (HADS-D).
4. Change from baseline to Week 8 on the DARS
5. Change from baseline to Week 8 on the SHAPS (using the original 0 – 14 scoring method and also using an alternative scoring method ranging from 14 – 56)

The following secondary endpoints will be used to assess the proportion of responders. They will be analyzed by logistic regression with fixed effects for treatment and investigative site with the addition of the baseline Investigator-administered MADRS as a covariate.

Responder rates defined by:

6. Proportion of patients who demonstrate clinical response, where **response** was defined by a reduction of at least 50% in the baseline Investigator-administered MADRS total score at Week 8.
7. Proportion of patients with MDD who achieved remission, where **remission** was defined by a total score of  $\leq 10$  on the Investigator-administered MADRS at Week 8.
8. Proportion of patients who demonstrate significant clinical improvement, where **improvement** is defined by a score of 1 (very much improved) or 2 (much improved) on the CGI-I at Week 8.

The following secondary efficacy endpoints based on the performance tasks will be analyzed and presented in summary and graphical displays.

Data for the FERT will be summarized (mean, standard deviation, range) for each treatment group at each visit. All treatment differences will be estimated with 95% CI. No adjustments will be made for multiple comparisons. The analysis will employ ANOVA models without adjusting for covariates. However, if significant confounds are identified, a secondary analysis will be performed to examine the relationship between FERT outcome measures and other covariates. A full description of the statistical analysis methods for FERT outcome measures will be provided in in the SAP.

9. Outcome measures from the FERT
  - a) Accuracy
  - b) Misclassification
  - c) Average reaction time
  - d) Target sensitivity
  - e) Response bias

Data for all PRT outcome measures will be summarized (mean, standard deviation, range) for each treatment group at each visit. The ANOVA models will be used to compare between treatment groups. For “Response bias” and “Discriminability,” treatment group, block, and treatment-by-block interactions will be considered fixed effects. For “Reaction time” and “Hit rates,” the stimulus type will be included as an additional fixed effect. The details of the analysis methods for these outcome measures will be described in the SAP.

10. Outcome measures from the PRT

- a) Response bias
- b) Discriminability
- c) Reaction time
- d) Hit rates

Data for all EEfRT outcome measures will be summarized (mean, standard deviation, range) for each treatment group at each visit. Statistical analyses of the Preference during the EEfRT trial will be performed using Generalized Estimating Equation (GEE) models. A binary logistic distribution will be used to model the probability of the Preference. The relationship and interactions between Preference and independent variables of reward magnitude, reward probability, expected value, age, sex, and efficacy parameters will be explored. The ANOVA model will be used to compare the completion rates between treatment groups. The details of the analysis method for these outcome measures will be described in the SAP.

11. Outcome measures from the EEfRT

- a) Preference (hard or easy task choice)
- b) Completion rates

13.2.8.4 EXPLORATORY EFFICACY AND HEALTH OUTCOMES ANALYSES

The exploratory endpoints will include:

1. Change in HAM-A total score from baseline to Week 4 and from baseline to Week 8
2. Change from baseline to Week 8 on the average pain in the last 24 hours.
3. Changes in plasma levels of nociceptin, and changes in serum levels of IL-1 $\beta$ , IL-2, IL-6, IL-10, TNF $\alpha$ , IFN $\gamma$ , and CRP from baseline to Week 8, correlated to treatment outcome and exposure

Exploratory endpoints will be summarized and, where appropriate, represented graphically. The analysis of the continuous exploratory endpoints will depend on the frequency of their measurements. If they are measured at baseline and multiple post-baseline visits, then an MMRM approach will be used. If they are measured at baseline and Week 8, an ANCOVA will be used. If the endpoint is only measured after treatment, an ANOVA will be used.

Further details on the analyses will be provided in the SAP.

#### 13.2.8.5 SENSITIVITY ANALYSIS

Analyses will be conducted to assess the validity of assumptions inherent to the primary analysis and to assess the sensitivity of results to untestable assumptions. The primary analysis will also be repeated using the Per-Protocol Analysis Set, the Completer Analysis Set, and the MADRS Non-responders at Week 2 Analysis Set. In addition, analyses will be conducted to assess the impact of missing data. Departures from the assumed missing at random mechanism will be assessed by implementing inclusive models for dropout within the multiple imputation frameworks. Full details of these analyses will be provided in the SAP.

#### 13.2.9 DIGITAL ASSESSMENTS

Vocal and behavioral digital assessment data are collected in this study. These data will be in a separate report.

#### 13.2.10 PHARMACOKINETIC/PHARMACODYNAMIC ANALYSES

Pharmacokinetic data collected in this study will be listed for the Pharmacokinetic Analysis Set. Population PK analysis of the plasma concentrations in this study will be reported separately. Pharmacokinetic data in this study may be combined with data from other studies to obtain improved model estimates and have adequate data for analysis.

Other exploratory analyses, such as the relationship between BTRX-246040 exposure and efficacy measures or AEs or other safety endpoints, may be undertaken as deemed appropriate.

#### 13.2.11 SAFETY ANALYSES

Safety assessments include AEs, SAEs, vital signs, weight and BMI, laboratory values, neurological exams, C-SSRS, SHSF, SHFU, and ECGs. All safety analyses will be performed on the Safety Analysis Set unless otherwise specified.

The safety/tolerability of BTRX-246040 and placebo will be compared for rates of spontaneously reported TEAEs, SAEs, AEs associated with self-harm episodes, early study discontinuations, discontinuations from BTRX-246040 or placebo, and AEs leading to discontinuation from the study or from BTRX-246040 or placebo.

Data will be pooled from all investigative sites for the analyses.

Safety results will be summarized by treatment. For categorical variables, frequencies and percentages will be reported and for continuous endpoints by visit and change from baseline summaries will be presented.

#### 13.2.12 SUBGROUP ANALYSES

Subgroup analysis based on gender, baseline severity of anhedonia symptoms (SHAPS total score  $\leq 4$  and  $> 4$ ; also SHAPS total score  $\leq 7$  and  $> 7$ ) and baseline severity of anxiety (HAM-A total score  $< 20$  and  $\geq 20$ ) will be performed. Subgroups based on other characteristics may be considered. All subgroup analyses will be exploratory in nature.

### 13.2.13 INTERIM ANALYSIS

No interim analyses are planned for this study.

## **14 INFORMED CONSENT, ETHICAL REVIEW, AND REGULATORY CONSIDERATIONS**

### **14.1 INFORMED CONSENT**

The Investigator is responsible for ensuring that the patient understands the potential risks and benefits of participating in the study, including answering any questions the patient may have throughout the study and sharing in a timely manner any new information that may be relevant to the patient's willingness to continue his or her participation in the trial.

The ICF will be used to explain the potential risks and benefits of study participation to the patient in simple terms before the patient is entered into the study, and to document that the patient is satisfied with his or her understanding of the risks and benefits of participating in the study and desires to participate in the study.

The Investigator is responsible for ensuring that informed consent is given by each patient. This includes obtaining the appropriate signatures and dates on the ICF prior to the performance of any protocol procedures and prior to the administration of investigational product.

### **14.2 ETHICAL REVIEW**

The Sponsor or its representatives must approve all ICFs before they are submitted to the IRB and are used at investigative sites(s). All ICFs must be compliant with the ICH guideline on GCP.

Documentation of IRB approval of the protocol and the ICF must be provided to the Sponsor before the study may begin at the investigative site(s). The IRB(s) will review the protocol as required.

Any member of the IRB who is directly affiliated with this study as an Investigator or as site personnel must abstain from the IRB's vote on the approval of the protocol.

### **14.3 REGULATORY CONSIDERATIONS**

This study will be conducted in accordance with:

1. consensus ethics principles derived from international ethics guidelines, including the Declaration of Helsinki and Council for International Organizations of Medical Sciences (CIOMS) International Ethical Guidelines
2. the ICH GCP Guideline [E6]
3. applicable laws and regulations.

The Sponsor certifies that this study is being conducted under an active US Investigational New Drug (IND) application.

Some of the obligations of the Sponsor will be assigned to a TPO.

#### 14.3.1 INVESTIGATOR INFORMATION

Physicians with a specialty in psychiatry or physicians with experience or with medical site staff with experience in treating MDD will participate as Investigators in this clinical trial.

#### 14.3.2 PROTOCOL SIGNATURES

The Sponsor's responsible medical officer will approve the protocol, confirming that to the best of his or her knowledge, the protocol accurately describes the planned design and conduct of the study.

After reading the protocol, each principal Investigator will sign the protocol signature page and provide a copy of the signed page to a Sponsor representative.

**Appendix 1 Examples of Inhibitors and Inducers of CYP3A4**

Per exclusion criterion 19: Are currently taking or have taken within 5 half-lives of Visit 2 (baseline) any medications or supplements that are strong inhibitors or inducers of CYP3A4. The listed moderate inhibitors/inducers below are not exhaustive. See also:

<http://www.fda.gov/drugs/developmentapprovalprocess/developmentresources/druginteractionslabeling/ucm093664.htm>.

**Table 1.a Inhibitors of CYP3A4**

Strong inhibitors a	Moderate inhibitors b
boceprevir	amprenavir
clarithromycin	aprepitant
conivaptan	atazanavir
grapefruit juice	ciprofloxacin
indinavir	darunavir
itraconazole	diltiazem
ketoconazole	erythromycin
lopinavir	fluconazole
mibefradil	fosamprenavir
nefazodone	imatinib
nelfinavir	verapamil
posaconazole	
ritonavir	
saquinavir	
telaprevir	
telithromycin	
voriconazole	

a Increases the area under the curve (AUC) of the substrate by  $\geq$  5-fold.

b Increases the AUC of the substrate by 2- to 5-fold.

**Table 1.b Inducers of CYP3A4**

Strong inducers a	Moderate inducers b
avasimibe	bosentan
carbamazepine	efavirenz
enzalutamide	
phenytoin	etravirine
rifampin	modafinil
St John's wort	nafcillin

a Decreases the AUC of the substrate by  $\geq 80\%$ .

b Decreases the AUC of the substrate by 50–80%.

## MODIFICATION HISTORY

Unique Identifier for this Version	Date of the Document Version	Author	Significant Changes from Previous Authorized Version
0.1		[name]	First Draft
0.2		[name]	Second Draft – Updates based on BlackThorn Review and Dry Run findings
0.3		[name]	Third Draft – Updates based on BlackThorn Review and Dry Run findings
1.0		[name]	Final Draft – updates based on DR2 and client updates

---

Document: C:\Users\q718413\Documents\NEP-MDD-201\_SAP\_v1.0\_Final\_06Dec2018.docx  
Author: [name]  
Version Number: 1.0  
Version Date: 06Dec2018

Template No: CS\_TP\_BS016 Revision 4  
Effective Date: 01Apr2016  
Reference: CS\_WI\_BS005

Copyright © 2009, 2010, 2012, 2016 Quintiles Transnational Corp. All rights reserved.  
The contents of this document are confidential and proprietary to Quintiles Transnational Corp. Unauthorized use, disclosure or reproduction is strictly prohibited.

Analysis Plan

---

## 1. INTRODUCTION

This document describes the rules and conventions to be used in the presentation and analysis of efficacy and safety data for Protocol NEP-MDD-201. It describes the data to be summarized and analyzed, including specifics of the statistical analyses to be performed.

This statistical analysis plan (SAP) is based on protocol version 6.0, dated 20 November 2018.

## 2. STUDY OBJECTIVES

### 2.1. PRIMARY OBJECTIVE

The primary objective is to evaluate the effects of BTRX-246040 on symptoms of depression in adult patients with Major Depressive Disorder after 8 weeks of double-blind treatment.

### 2.2. SECONDARY OBJECTIVES

The secondary objectives are as follows.

- To evaluate the effects of BTRX-246040 on anhedonia in adult patients with MDD.
- To evaluate the safety and tolerability of BTRX-246040 in adult patients with MDD.
- To evaluate the effects of BTRX-246040 on the performance of tasks as measured by the Facial Expression Recognition Task (FERT), Probabilistic Reward Task (PRT), and Effort Expenditure for Reward Task (EEfRT) in adult patients with MDD.

### 2.3. EXPLORATORY OBJECTIVES

The exploratory objectives are as follows.

- To evaluate the effects of BTRX-246040 on anxiety-related symptoms in adult patients with MDD.
- To evaluate the effects of BTRX-246040 on pain-related symptoms in adult patients with MDD.
- To evaluate the effects of BTRX-246040 as measured by biomarkers in adult patients with MDD.

---

Document:	C:\Users\q718413\Documents\NEP-MDD-201_SAP_v1.0_Final_06Dec2018.docx		
Author:	[name]	Version Number:	1.0
		Version Date:	06Dec2018

Template No: CS\_TP\_BS016 Revision 4  
Effective Date: 01Apr2016

Reference: CS\_WI\_BS005

Copyright © 2009, 2010, 2012, 2016 Quintiles Transnational Corp. All rights reserved.  
The contents of this document are confidential and proprietary to Quintiles Transnational Corp. Unauthorized use, disclosure or reproduction is strictly prohibited.

[figure not shown]

Analysis Plan

### 3. STUDY DESIGN

#### 3.1. GENERAL DESCRIPTION

Study NEP-MDD-201 is an 8-week, randomized, double-blind, placebo-controlled, parallel group, multicenter study. There will be a 28-day screening period, 8-week active treatment period (during which patients will receive either BTRX-246040 or placebo), and an approximate 1- to 2-week off-drug safety follow-up period (Figure 1).

**Figure 1: Study Design**

Patients will be consented and screened for the study until approximately 100 patients are randomized. Randomization will be performed at Visit 2 (baseline) in a 1:1 ratio to one of two treatment arms (placebo or BTRX-246040 QD) after meeting disease diagnostic criteria for MDD and study inclusion (see section 8). Randomization will be stratified by anhedonia symptom severity, as indicated by a SHAPS total score  $\leq 4$  and  $> 4$ .

#### 3.2. SCHEDULE OF ASSESSMENTS

The schedule of assessments can be found in [Table 1](#) in Section 9.8 of the protocol.

#### 3.3. CHANGES TO ANALYSIS FROM PROTOCOL

There are no planned changes from the protocol.

---

Document: C:\Users\q718413\Documents\NEP-MDD-201\_SAP\_v1.0\_Final\_06Dec2018.docx  
 Author: [name]  
 Version Number: 1.0  
 Version Date: 06Dec2018

Template No: CS\_TP\_BS016 Revision 4  
 Effective Date: 01Apr2016  
 Reference: CS\_WI\_BS005

Copyright © 2009, 2010, 2012, 2016 Quintiles Transnational Corp. All rights reserved.  
 The contents of this document are confidential and proprietary to Quintiles Transnational Corp. Unauthorized use, disclosure or reproduction is strictly prohibited.

## 4. PLANNED ANALYSES

There are no analyses for data monitoring committees or interim analyses planned for this study. Thus, the only analysis planned for this study is the final analysis following database lock.

### 4.1. DATA MONITORING COMMITTEE (DMC)

There will be no DMC for this study.

### 4.2. INTERIM ANALYSIS

There will be no interim analysis for this study.

### 4.3. FINAL ANALYSIS

All final, planned analyses identified in this SAP will be performed by IQVIA Biostatistics following sponsor authorization of this statistical analysis plan, database lock, sponsor authorization of analysis sets and unblinding of treatment groups.

## 5. ANALYSIS SETS

Agreement and authorization of patients included/excluded from each analysis set will be conducted prior to the unblinding of the study. The analysis for the Full-Analysis Set population defined in [section 5.3](#) will be performed according to the treatment patients were randomized to. All other analyses will be performed according to the treatment the patient received.

### 5.1. ALL PATIENTS ENROLLED SET [ENR]

The all patients enrolled (ENR) set will contain all patients who provide informed consent for this study.

### 5.2. ALL PATIENTS RANDOMIZED SET [RND]

The all patients randomized (RND) set will contain all patients in the ENR set who were randomized to study medication.

---

Document:	C:\Users\q718413\Documents\NEP-MDD-201_SAP_v1.0_Final_06Dec2018.docx	Version Number:	1.0
Author:	[name]	Version Date:	06Dec2018

Template No: CS\_TP\_BS016 Revision 4  
Effective Date: 01Apr2016

Reference: CS\_WI\_BS005

Copyright © 2009, 2010, 2012, 2016 Quintiles Transnational Corp. All rights reserved.  
The contents of this document are confidential and proprietary to Quintiles Transnational Corp. Unauthorized use, disclosure or reproduction is strictly prohibited.

### 5.3. FULL ANALYSIS SET [FAS]

The full analysis set (FAS) will contain all patients in the RND set who received at least one dose of study medication and have at least one post-dose efficacy assessment. The intent-to-treat principle is preserved, despite the exclusion of patients randomized who did not take the study medication or do not have post-baseline efficacy data, because the decision of whether or not to begin the treatment could not be influenced by knowledge of the assigned treatment due to the study blinding.

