## 13 SAMPLE SIZE AND STATISTICAL METHODS

### 13.1 DETERMINATION OF SAMPLE SIZE

The sample size determination was based on the primary endpoint, change from baseline in the Investigator-administered MADRS total score, at Visit 7 (week 8). Approximately 100 patients will be randomized to either BTRX-246040 or placebo in a 1:1 allocation ratio. A sample size of 44 patients per treatment group will provide 75% power to detect a relative effect size of 0.5 on the MADRS total score, based on a two-sample t-test and a significance level of 0.10. All tests are two-sided. To account for patients who may discontinue early and be excluded from the analysis population, a sample size of approximately 50 patients per treatment group (total of 100 patients) will be randomized.

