#### 15.1.4. SENSITIVITY ANALYSIS OF PRIMARY EFFICACY VARIABLE

The following sensitivity analyses will be conducted on the change from baseline in investigator-administered MADRS total score to ensure robustness of the primary efficacy analysis. The FAS will be used for all sensitivity analyses unless otherwise specified.

- The primary efficacy analysis will be repeated on the PPAS, CAS, and MNRAS analysis sets.
- The MMRM model used for the primary efficacy analysis will be used to analyze the change from Baseline in investigator-administered MADRS total score at each post-Baseline visit. For each visit the difference in LS Means between BTRX-246040 and placebo will be presented alongside the 2-sided 95% confidence interval and P-value.
- ANCOVA will be used to analyze the change in investigator-administered MADRS total score from baseline to week 8, with missing data imputed. The ANCOVA model will include treatment group, investigative site as fixed effects and baseline investigator-administered MADRS total score as a covariate. Only the MADRS total score will be imputed where missing, the individual component scores will not be imputed. Imputation will be performed following visit window remapping. The following two methods of data imputation will be used:
  - Multiple imputation using Rubin's rules with SAS Proc MI and MIANALYSIS.
  - Single imputation by last observation carried forward (LOCF).
- Finally, the change from baseline in the computer-administered MADRS total score will be analyzed using the same method as the primary efficacy analysis.

Forest plots of the treatment difference and confidence intervals will be created for the primary analysis and each of the efficacy analyses.

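### The SAP says the FAS preserves intent-to-treat, but its blinding reason does not cover patients dosed and lost before any efficacy assessment, and no planned efficacy analysis tests leaving them out

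*SAP*

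**What the plan says.** SAP 5.3 admits to the FAS those randomized patients who "received at least one dose of study medication and have at least one post-dose efficacy assessment". Two groups therefore fall out, and the section names both: patients who "did not take the study medication or do not have post-baseline efficacy data". It says of both that intent-to-treat still holds, in a sentence that opens "The intent-to-treat principle is preserved, despite the exclusion of patients randomized who did not take the study medication" and goes on to the second group. The reason given is a single one: "because the decision of whether or not to begin the treatment could not be influenced by knowledge of the assigned treatment", owing to the blinding.

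SAP 15.1.4 then sets the scope of the robustness work: "The FAS will be used for all sensitivity analyses unless otherwise specified". Neither imputation ANCOVA names another set. One is "Multiple imputation using Rubin's rules with SAS Proc MI and MIANALYSIS"; the other is LOCF. The remaining efficacy sets (per-protocol, completers, Week 2 non-responders; SAP 5.4, 5.7, 5.8) are all drawn from the FAS. Protocol 13.2.2 defines the FAS in the same way and makes it the default for efficacy.

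Protocol 13.2.8.5 promises an assessment of departures from missing at random within multiple imputation and leaves the detail to the SAP. The SAP specifies no such analysis, while SAP 3.3 records no changes from the protocol.

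SAP 9 plans a summary of membership of every analysis set by arm for the randomized set, and reasons for discontinuation by arm.

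**The concern.** The conclusion in SAP 5.3 is wider than its reason. Blinding makes the choice to take a first dose independent of assignment. It does not make what follows the first dose independent of assignment, because a blinded patient can still leave on account of what the drug does. Patients dosed and never assessed are therefore a post-exposure exclusion, and the stated property is not established for them.

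The route exists in this trial. The first dose is taken after all Visit 2 procedures, the next scheduled efficacy visit is Day 8, and Protocol 7.1 provides for discontinuation of patients who cannot tolerate the starting dose. Protocol 5 reports that in the earlier MDD study nausea (10.1% vs 1.5%), insomnia (10.1% vs 0) and dizziness (7.2% vs 0) were more frequent on drug.

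These patients cannot contribute post-baseline data to the MMRM, so the primary model is not the issue. The imputation ANCOVAs exist to probe missing data, yet they omit the patients who have the least data. A reader told that intent-to-treat is preserved would have no reason to ask about them.

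**Working it through.** **The plan's own figure first.** Protocol 13.1: 44 per group, effect size 0.5, two-sided alpha 0.10, two-sample t-test. The noncentrality is 0.5 × √(44/2) = 2.345 on 86 degrees of freedom. Power is 75.2% (noncentral t) or 75.8% (normal approximation), against a stated 75%, so it reproduces. The step to 50 per group is an allowance of (50 − 44)/50 = 12%. Nothing here disputes that calculation.

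**Who is covered by what.**

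| Group | Covered by the blinding reason? | In any planned efficacy analysis? |
|---|---|---|
| Randomized, never dosed | Yes | No |
| Dosed, no post-dose efficacy assessment | No | No |
| Dosed, at least one post-dose efficacy assessment | Not needed | Yes (FAS) |

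**Illustration of size.** The documents give neither a count for the second group nor an SD, so these inputs are assumptions: 50 dosed per arm, a difference of 5 points (or 0.5 SD) among assessed patients, and a placebo change p of −10 to −14, which puts the assessed active change at a = p − 5. Let kA and kP be the numbers excluded, and eA and eP the changes those patients would have had. Then

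FAS difference − all-dosed difference = (kA/50)(a − eA) − (kP/50)(p − eP).

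*Excluded patients at the placebo mean (eA = eP = p).* The all-dosed effect is 0.5 × (50 − kA)/50, and placebo exclusions have no influence.
- kA = 1: 0.5 × 49/50 = 0.49 SD, a shortfall of 2%.
- kA = 4: 0.5 × 46/50 = 0.46 SD, a shortfall of 8%.

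*Excluded patients with no change (eA = eP = 0).* Each arm mean is (50 − k)/50 times its assessed mean.

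| Excluded (active/placebo) | p = −10 | p = −14 | Shortfall as share of 5 points |
|---|---|---|---|
| 1 / 0 | −14.70 + 10.00 = −4.70 | −18.62 + 14.00 = −4.62 | 6% to 7.6% |
| 4 / 1 | −13.80 + 9.80 = −4.00 | −17.48 + 13.72 = −3.76 | 20% to 24.8% |
| 0 / 1 | −15.00 + 9.80 = −5.20 | −19.00 + 13.72 = −5.28 | none: FAS understates by 4% to 5.6% |

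The last row shows that the sign depends on which arm loses patients.

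**Which imputation can show it.** Under missing at random with treatment in the model, a patient with only a baseline value is imputed around the expected value for that arm given baseline. Adding such patients leaves the expected treatment difference essentially where it was. LOCF has no post-baseline value to carry. Of the planned methods, only a version that carries baseline forward (change 0) moves the estimate.

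**The case against.** The strongest reply is that little is hidden and few patients are involved. Much of it stands.

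- **Visibility.** A reader might infer that these losses would go unseen. They would not: the SAP 9 set summary allows the Safety set minus the FAS to be read off by arm, and discontinuation reasons are planned. What is missing is an efficacy analysis that includes these patients, and reasons reported for this group in particular.
- **Narrowness.** Early leavers are encouraged to complete the end-of-treatment assessments (Protocol 8.3.1, 9.7), and SAP 6.3 and 6.4 map early-termination MADRS data from Days 2 to 11 to Week 1. At Visit 3 the MADRS also comes before the dose increase (Protocol 9.3). Only patients who never return for any efficacy assessment are lost.
- **Adverse events.** The quoted rates might be read as evidence of first-week dropout on drug. They are incidences from an 8-week study, without onset times, and most events were mild or moderate. They make the route plausible and no more.
- **The 12% allowance.** This might be taken as the expected or maximum size of the group. Protocol 13.1 gives it a general purpose, "To account for patients who may discontinue early and be excluded from the analysis population", so it neither forecasts nor bounds this group.
- **Openness.** The SAP names the second exclusion, and the FAS is analysed as randomized (SAP 5).
- **Stage.** This is a Phase 2a study looking for trends, and the primary analysis would not change.

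None of this supplies a reason for calling intent-to-treat preserved in patients who were dosed and not assessed.

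**Conclusion.** The point holds as a defect of justification and coverage. SAP 5.3 claims a property for two exclusions and supports it for one, and no planned efficacy analysis tests the other.

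It would go too far to say that the exclusion favours the active arm. That requires losses to be more frequent on drug and the lost patients to do worse than those assessed, and the documents establish neither. The illustrative overstatement is about 2-8% of the effect if 1 to 4 excluded active patients resemble the placebo mean. It is about 6-25% if excluded patients do not change, where the upper end also assumes one placebo exclusion and a placebo change of −14. These ranges rest on 50 per arm and on chosen counts and outcomes, and with losses on placebo only the sign reverses. The real size may be negligible.

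**What to change.** 1. In SAP 5.3, delete the intent-to-treat statement or limit it to never-dosed patients.
2. Keep the primary MMRM on the FAS.
3. In SAP 15.1.4, run the single-imputation ANCOVA additionally on all randomized, dosed patients, with change 0 (baseline carried forward) for those with no post-dose MADRS, labelled as a conservative sensitivity analysis. State that it is analysed as randomized, because SAP 5 otherwise analyses sets other than the FAS by treatment received.
4. If multiple imputation is extended to this set, give these patients a missing-not-at-random assumption, in line with Protocol 13.2.8.5. Enlarging the set under missing at random would not be expected to reveal the problem.
5. Beside these results, report the number with no post-dose MADRS by arm and reason. This can slightly exceed the SAP 9 difference, since any efficacy assessment qualifies a patient for the FAS.

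The cost is a wording change, one further run of a planned ANCOVA and a short table, all from data already collected. The downside is that the sensitivity estimate may be slightly less favourable.
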